**C11a. Outcomes:**

**Primary outcomes:**

1. **Average expired carbon monoxide over the last 24 hours in the hotel.** Carbon monoxide is on the FDA's list of harmful and potentially harmful constituents (19). Expired carbon monoxide can be measured intensively in this setting and is a well-validated measure of smoke exposure.
2. **the total number of cigarettes smoked at the hotel** (defined as the # cigarettes purchased at the hotel *minus* # returned at the end of the hotel stay)

**Secondary outcome:**

1. total number of cigarettes smoked at the hotel (defined as the number of cigarette butts collected during the hotel stay)
2. total puff volume (puff count \* average puff volume for a single cigarette smoked through the CReSS micro device on Hotel Day 5)
3. Cotinine (the primary metabolite of nicotine) at baseline and Day 5 using urine to describe nicotine exposure and calculate a compensation index (i.e., the logarithmic change in nicotine exposure given the logarithmic change in nicotine content between products). The final urinary cotinine sample will also be utilized to confirm exclusive use of VLNC cigarettes in the VLNC condition (<2.69 nmol/ml, (1)). Cotinine analyses will be conducted by the Clinical Neuroscience Laboratory at the Medical University of South Carolina. Aliquots of all urine samples will be stored at the Clinical Neuroscience Laboratory for the possibility of conducting additional analyses if needed.
4. Withdrawal (MNWS) scores
5. Depressioning symptoms (CESD)
6. Craving (QSU) of both study cigarettes and usual brand cigarettes
7. Demand (parameters derived from purchase task) for usual brand and study cigarettes
8. Product appeal and reward (CES)
9. Changes in dependence (FTND and WISDM)

**C11b Storage of biological specimens.** Urine samples will be stored for future analysis. A section has been added to the consent form clearly describing the storage of biological specimens. Samples will be stored in the Clinical Neuroscience Laboratory at the Medical University of South Carolina. Samples will be deidentified. We will also store collected cigarette butts for potential future analysis.

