### **A2. Compensation as a result of nicotine reduction**

A critical concern regarding a mandatory nicotine reduction policy is that smokers might increase their smoke intake—either through increases in cigarettes smoked per day or changes in how they smoke cigarettes—to obtain more nicotine (i.e., compensation), negatively impacting public health. It is well known

[figure not shown]
that when smokers switch to highly ventilated cigarettes that deliver less nicotine (i.e., light cigarettes), they compensate for the reduction in nicotine yield, largely maintaining their nicotine exposure (4). However, data regarding VLNC cigarettes, which have a much lower nicotine yield as a result of a large reduction in the actual nicotine content of the cigarette, are less clear. Acute laboratory studies have shown that when smokers switch to VLNC cigarettes, they engage in compensatory changes in smoking behavior for the first few cigarettes (6, 7). However, clinical trials have not shown a sustained increase in smoke exposure associated with VLNC cigarettes (3, 8, 9). One possible reason that smokers in clinical trials do not compensate for the loss in nicotine may be that they can easily access normal nicotine content cigarettes.

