### **C7. Procedures**

Study participation consists of a screening visit and two four-night stays in the hotel.

**C7a. Screening visit.** After obtaining informed consent, screening assessments will be completed (measures described below). At the end of the session, eligible participants will be scheduled for two hotel stays. It will be stressed to participants that it is critical that they attend both hotel stays, and we have provided a completion bonus to maximize the likelihood of study completion. In our prior study (1), 100% of our participants completed the entire hotel protocol. A baseline puff topography assessment will be completed for eligible participants using participants’ usual brand cigarette. Puff topography provides an analysis of smoking behavior including changes in the rate or volume of inhalation which can influence smoke exposure and nicotine delivery of cigarettes.

**C7b. Hotel phase.** Participants will return to the lab on the morning of each hotel stay. Participants will complete a Timeline Follow Back Assessment about their tobacco use over the previous 14 days, and we will collect a first void urine for baseline assessment. We will also obtain an expired carbon monoxide sample.

Participants will arrive at the hotel and have their first opportunity to buy cigarettes at 4PM on Hotel Day 1. While at the hotel, participants will have “check in” times of 8AM, 12PM, 4PM, and 8PM. Check-ins will be used to collect physiological assessments, collect self-report questionnaires, and for participants to purchase more cigarettes if needed. Measures at the hotel are designed to assess the safety of the participants using the study product, the impact of nicotine reduction on physiological and behavioral measures of smoke exposure, and the impact of nicotine reduction on other key measures like withdrawal, craving, and reinforcement value. Participants will return all unused cigarettes and depart the hotel at 12PM on Hotel Day 5. Participants will spend approximately 96 hours (four 24-hr periods) in the hotel. A puff topography assessment will be completed each day by having participants smoke one of the research cigarettes through a device that measures how they smoke cigarettes. Puff topography provides an analysis of smoking behavior including changes in the rate or volume of inhalation which can influence smoke exposure and nicotine delivery of cigarettes.

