**C12. Statistical analysis, power calculations and predicted outcomes**

For *Aim 1*, we will test the impact of cigarette nicotine content on physiological measures of smoke exposure using a linear mixed model with fixed effects for nicotine content, period, and order, and random effects for subject and group. Physiological outcomes are expected to be skewed and will be log transformed. The *primary outcome* is average expired carbon monoxide over the last 24 hours. A secondary analysis will be conducted using the area under the curve (AUC) for expired carbon monoxide across time points. For *Aim 2*, we will test whether nicotine reduction impacts behavioral measures of smoking behavior using the approach described above. Outcomes include average cigarettes smoked per day (total hotel cigarettes / 4) and total puff volume.

We will conduct exploratory tests of the impact of menthol status and gender on each outcome, although we are not powered to detect these effects. Future studies may follow up on gender or menthol effects we observe but cannot detect statistically. The within-subjects design should minimize variability, but we will collect baseline measures for all key outcomes, which can be included in analyses if necessary.

A power analysis revealed that a sample size of 20 smokers will provide 80% power to detect an effect size of 0.65 with an alpha of 0.05, which would correspond to a 20% increase in expired carbon monoxide (note we may enroll up to 50 participants in expectation of participants who do not meet eligibility criteria or withdraw). A 20% change in smoke exposure is consistent with the increase in smoke exposure and cigarettes smoked per day that is observed in experimental studies where smokers are switched to a cigarette with a lower nicotine yield (i.e., a light cigarette) (4, 19, 20). This sample size will provide power to detect a similar increase in remaining outcomes including cigarettes smoked per day and total puff volume.

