**C13. Scientific rigor considerations**

Each participant will serve as their own control by completing a VLNC and NNC condition, in which all variables are held constant except the nicotine content of Spectrum cigarettes and the information that participants receive about nicotine content. Study staff will follow detailed protocols and scripts to standardize procedures. The order of conditions will be counterbalanced between the sets of 10 participants that complete the hotel stays together. Analyses will follow an a priori statistical analysis plan including rules for identifying

outliers and the use of a blinded third party for data cleaning as needed. Sample size was determined via a power analysis.

**C14. The National Institutes of Health now considers all ongoing clinical research to be in possession of a Certificate of Confidentiality.** With this certificate, the researchers cannot be forced to disclose information that may identify the participants, even by a court subpoena, in any federal, state, or local civil, criminal, administrative, legislative, or other proceedings. The researchers will use the Certificate to resist any demand for information that would identify the participants, except as explained below. The certificate cannot be used to resist a demand for information from personnel of the United States Government that is used for auditing or evaluation of federally funded projects or for information that must be disclosed in order to meet requirements of the Federal Food and Drug Administration. The Certificate of Confidentiality does not prevent the participant or a member of their family from voluntarily releasing information about themselves and their involvement in the research. If an insurer, employer, or other person obtains the participant's written consent to receive research information, then the researcher may not use the Certificate to withhold that information. The Certificate of Confidentiality does not prevent the researchers from disclosing voluntarily, without consent, information that would identify the individual as a participant of the research project in instances such as evidence of child abuse or a participant's threatened violence to self or others.

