### **b. Primary and Secondary Outcome Measures**

The primary outcome for Aim 1 is expired carbon monoxide. The primary outcomes for Aim 2 will be average cigarettes smoked per day and total puff volume as assessed using puff topography. Other outcomes of interest include urinary cotinine, cigarette butt weight, the Minnesota Withdrawal Scale, the Questionnaire of Smoking Urges score, the Cigarette Evaluation Scale, the Cigarette Purchase Task, the Perceived Health Risks Questionnaire, the Fagerström Test for Nicotine Dependence, the Wisconsin Inventory of Smoking Dependence Motives, and the Smoking Consequences Questionnaire-Adult.

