### **d. Power Analysis and Sample Size**

Our goal is to enroll 20 participants who complete the Hotel Phase. We may consent up to 50 participants because we expect that approximately 50% of participants will not be eligible to participate after screening, and that 10% may lose interest or withdraw prior to the hotel phase. We assume that 100% of participants who initiate the hotel phase will complete the study based on our prior hotel study which had a 100% completion

rate. Up to four additional participants will be recruited to serve as alternates during the hotel phase in case another eligible participant is unexpectedly unable to attend the hotel phase.

Primary outcomes for Aim 1 is expired carbon monoxide. Carbon Monoxide is expected to be skewed and will be log transformed. The primary outcomes for Aim 2 are cigarettes smoked per day and total puff volume. This study is powered to detect an increase in smoke exposure of 20%. Our effect size for this power analysis was taken from the existing literature on “light” cigarettes and the increase in smoke exposure produced for light cigarettes. For example, in a recent paper from [name] lab (2), switching to light cigarettes produced an increase in cigarettes smoked per day from 22.5 CPD to 27.5 CPD (22% increase). A predicted increase in exposure of 20% is conservative in that compensation for VLNC cigarettes, if present, is likely to be much larger than compensation for light cigarettes because the reduction in nicotine yield for VLNC cigarettes is much larger than the reduction in nicotine yield for light cigarettes.

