### **c. Data Analysis Plan**

Data analysis will be completed by [name].

The primary statistical analysis will use linear mixed model with fixed effects for nicotine content, period, and order, and random effects for subject and group. The type-1 error rate will be 0.05. Continuous outcomes will be summarized by the mean, standard deviation, median and range, while categorical outcomes will be summarized by frequencies and percentages. Skewed continuous outcomes will be log-transformed or square root-transformed as appropriate; for example we conventionally analyze cotinine on log scale.

Biomarkers will be analyzed in a natural log scale such that the model assumptions of normality and equal variances can hold, and geometric means in original units will be calculated as well. A p-value < 0.05 would be conventionally used as “statistical significance”.

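### Total puff volume is secondary in one section and primary for Aim 2 in two others, and the planned model's period and order terms cannot be estimated under the fixed stay order

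*Combined protocol and SAP*

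**What the plan says.** **Status of the outcome.** C11a names two primary outcomes: expired carbon monoxide (CO) averaged over the final 24 hours, and total cigarettes smoked in the hotel (purchased less returned). Total puff volume is item 2 under the secondary heading, computed as puff count times "average puff volume for a single cigarette smoked through the CReSS micro device on Hotel Day 5". The DSMP, part of the same document, differs. Section 1b states: "The primary outcomes for Aim 2 will be average cigarettes smoked per day and total puff volume as assessed using puff topography". Section 1d repeats it: "The primary outcomes for Aim 2 are cigarettes smoked per day and total puff volume".

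**Model.** C12 specifies a linear mixed model for Aim 1 with fixed terms for nicotine content, period and order and random terms for subject and group, and carries the same approach over to Aim 2. DSMP 3c repeats that model as the primary analysis. C13 describes condition order as counterbalanced between the two sets of 10 participants. The note at the front of the protocol says that this was not done: every participant had the normal-nicotine (NNC) stay and then the very-low-nicotine (VLNC) stay.

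**Power.** C12 gives 80% power with 20 smokers at an effect size of 0.65 and alpha 0.05, and equates this with a 20% rise in CO. It then adds: "This sample size will provide power to detect a similar increase in remaining outcomes including cigarettes smoked per day and total puff volume". No SD for puff volume appears in the supplied text. On scale, DSMP 3c says: "Skewed continuous outcomes will be log-transformed or square root-transformed as appropriate".

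**Collection.** C7b provides for more readings than the outcome uses: "A puff topography assessment will be completed each day by having participants smoke one of the research cigarettes through a device".

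**The concern.** Total puff volume is the plan's direct measure of how each cigarette is puffed, and a change in puffing is one of the two routes of compensation that the protocol sets out to detect. If its status is open, a positive or negative puff-volume result can be given primary or secondary weight after the data are seen.

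The model matters more widely, because it is the stated analysis for every main outcome. If two of its fixed effects cannot be estimated, software will either fail or silently drop a column, and which column goes depends on the package and the order of entry. A reader shown a condition effect from a model described as adjusted for period and order would believe that time effects had been removed. They cannot have been.

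The power sentence is a lesser matter. It offers reassurance for an outcome whose variability is not given.

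**Working it through.** **1. Status, section against section.**

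| Section | Primary | Total puff volume |
|---|---|---|
| C11a | CO; total cigarettes (purchased less returned) | Secondary, item 2 |
| DSMP 1b | CO (Aim 1); cigarettes per day and total puff volume (Aim 2) | Primary for Aim 2 |
| DSMP 1d | As 1b | Primary for Aim 2 |

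All three are current text, not a record of superseded wording. They cannot all hold.

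**2. Can the fixed effects be estimated?** Take 20 participants with two stays each, and four fixed-effect columns: intercept, condition (0 = NNC, 1 = VLNC), period (0 = first stay, 1 = second) and order (0 = NNC first, 1 = VLNC first).

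- Under the fixed order, every first-stay row is (1, 0, 0, 0) and every second-stay row is (1, 1, 1, 0). Condition and period are the same column, and order is constant and so adds nothing to the intercept. The rank is 2 of 4.
- With one set of 10 in each order, as C13 describes, the rank is 4 of 4. The model was estimable for the counterbalanced design and stopped being so when the order was fixed.

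Write the condition effect as β and the period effect as π. Each participant's VLNC minus NNC difference then has mean β + π. Only this sum is identified; no choice of model recovers β alone. The planned random subject and group effects are not the difficulty: both are common to a participant's two stays and cancel from that difference.

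**3. The power claim.** Inputs from C12: n = 20, effect size d = 0.65, alpha 0.05, a 20% increase. Assumptions: two-sided test (C12 does not state sidedness), paired t, log scale.

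- *The plan's own figure.* Noncentrality = 0.65 × √20 = 2.907, df = 19, critical t = 2.093. Power = 78.7%, which agrees with the stated 80% to within rounding.
- *SD implied for CO.* ln(1.20) / 0.65 = 0.1823 / 0.65 = 0.280. Exactly 80% power needs d = 0.660, so SD = 0.1823 / 0.660 = 0.276.
- *Puff volume.* Its SD is not given, so a range is shown for a 20% increase, with d = 0.1823 / SD:

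| Paired log-difference SD (assumed) | d | Power |
|---|---|---|
| 0.25 | 0.729 | 87% |
| 0.28 | 0.651 | 79% |
| 0.35 | 0.521 | 60% |
| 0.42 | 0.434 | 45% |

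The figure of 0.28 is back-calculated from the CO statement. The documents do not offer it for puff volume, and C12 attaches no power level to that outcome.

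**The case against.** **The single Day 5 cigarette.** A reader might infer that resting the outcome on one cigarette per stay, while daily readings go unused, is a flaw that costs precision. The documents do not support that. Day 5 is a coherent end-of-stay target, in line with the timing of the CO and cotinine outcomes. Section A2 gives a reason to avoid early readings: on switching to VLNC cigarettes, smokers in acute studies were found to change, in that "they engage in compensatory changes in smoking behavior for the first few cigarettes". An average over several days would estimate a different quantity and could gain or lose power, depending on day-to-day correlations that the documents do not give. It would also be a weak check on Day 5. Suppose the effect averaged over Days 3 to 5 is 80% of the Day 5 effect, with d = 0.65 on Day 5. The power to detect that gap with 20 pairs is then only about 12%, 16%, 33% or 57% at assumed between-day correlations of 0.25, 0.5, 0.8 or 0.9. Nor can absence be proved, since C13 says: "Analyses will follow an a priori statistical analysis plan including rules for identifying" outliers, and that plan is not reproduced here.

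**The order change is disclosed.** This is true and to the protocol's credit. But the note changes only the order and the participant wording; it says nothing of the model, and C12, C13 and DSMP 3c still describe the counterbalanced design. The unseen analysis plan may have adapted the model, but that would not correct the text that readers have.

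**The power sentence is loose rather than wrong.** This stands. It states no power level for puff volume, so it is unsupported, not shown to be false. Saying that it fails above an SD of 0.28 would carry over the 80% that the plan states for CO only.

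**Conclusion.** Two statements are wrong as written. First, total puff volume cannot be both secondary (C11a) and primary for Aim 2 (DSMP 1b and 1d). Second, the model in C12 and DSMP 3c cannot be estimated under the order actually used. Its fixed part has rank 2 of 4, and the condition contrast is inseparable from period for every outcome analysed this way. Both conclusions follow from the text and need no assumed figure. How large any period effect is, and in which direction it acts, cannot be learned from the documents.

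The puff-volume power claim is a minor, unsupported statement. The reference values (SD about 0.28 for about 80% power; about 60% power at 0.35) rest on a two-sided paired t-test, the log scale and 20 complete pairs. DSMP 3c also leaves a square-root scale open.

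Leaving the other daily topography readings out of the stated analysis is not a defect in the plan.

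**What to change.** 1. Give total puff volume one status throughout. The shortest route is to amend DSMP 1b and 1d to match C11a, so that it is clear which outcomes carry the Aim 2 conclusion.
2. In C12 and DSMP 3c, remove period and order, and fit condition with the planned random effects. Correct the counterbalancing statement in C13. State plainly that, because all participants had NNC before VLNC, the condition effect cannot be separated from period, and repeat this wherever results are reported.
3. In C12, either give an SD for total puff volume, with its source and the scale of analysis, or delete the power claim for that outcome.

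A descriptive summary of the other daily topography readings may be added as supportive material, with Day 5 still governing. It is optional.

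The cost is wording only, with no new data or visits. Removing period and order loses no information, since neither can be estimated. The confounding statement limits what the trial can claim, but that limit already follows from the design.

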**C12. Statistical analysis, power calculations and predicted outcomes**

For *Aim 1*, we will test the impact of cigarette nicotine content on physiological measures of smoke exposure using a linear mixed model with fixed effects for nicotine content, period, and order, and random effects for subject and group. Physiological outcomes are expected to be skewed and will be log transformed. The *primary outcome* is average expired carbon monoxide over the last 24 hours. A secondary analysis will be conducted using the area under the curve (AUC) for expired carbon monoxide across time points. For *Aim 2*, we will test whether nicotine reduction impacts behavioral measures of smoking behavior using the approach described above. Outcomes include average cigarettes smoked per day (total hotel cigarettes / 4) and total puff volume.

We will conduct exploratory tests of the impact of menthol status and gender on each outcome, although we are not powered to detect these effects. Future studies may follow up on gender or menthol effects we observe but cannot detect statistically. The within-subjects design should minimize variability, but we will collect baseline measures for all key outcomes, which can be included in analyses if necessary.

A power analysis revealed that a sample size of 20 smokers will provide 80% power to detect an effect size of 0.65 with an alpha of 0.05, which would correspond to a 20% increase in expired carbon monoxide (note we may enroll up to 50 participants in expectation of participants who do not meet eligibility criteria or withdraw). A 20% change in smoke exposure is consistent with the increase in smoke exposure and cigarettes smoked per day that is observed in experimental studies where smokers are switched to a cigarette with a lower nicotine yield (i.e., a light cigarette) (4, 19, 20). This sample size will provide power to detect a similar increase in remaining outcomes including cigarettes smoked per day and total puff volume.

